4.2 Secondary Objectives

1. To examine the following clinical outcomes for ACS patients managed with PCI initiating treatment with prasugrel versus those initiating treatment with clopidogrel:
 - a. To describe differences in the demographic, clinical, and angiographic profiles. To compare the composite MACE endpoint within 30, 180, and 365 days following index PCI.
 - b. To compare the individual components of the MACE endpoint (all-cause death, MI, stroke, and unplanned revascularization) within 30, 90, 180, and 365 days following index PCI.
2. To compare all in and out of hospital bleeding events within 30, 90, 180 and 365 days from index PCI. To compare bleeding-related rehospitalizations within 30, 90, 180, and 365 days from index hospital discharge with prasugrel versus clopidogrel
3. To compare post-procedural (in-hospital) MACE and bleeding events.
4. To compare Academic Research Consortium (ARC) defined definite/probable stent thrombosis at 30, 90, 180, and 365 days following index PCI with prasugrel versus clopidogrel.
5. To compare MACE and bleeding events at 30, 90, 180 and 365 days following index PCI in the following pre-specified subgroups:
 1. ACS-PCI patients with no prior transient ischemic attack (TIA) or stroke
 2. ACS-PCI patients with no prior TIA or stroke and are:
 - a. <75 years of age, or

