6.1 Methods

Primary Objective

The exposure groups for the primary analysis will be defined as those patients receiving prasugrel or clopidogrel at the time of PCI (i.e. loaded peri-procedurally or currently taking in the absence of a load). All patients will be assigned to one of these mutually exclusive groups irrespective of medication administered at discharge. Patients administered both medications at the time of PCI will be excluded for any comparative analyses of treatments.

For descriptive purposes, baseline clinical (including laboratory evaluations) and demographic and procedural characteristics will be compared between groups using student's t-test and chi-square test or Fisher's exact test for continuous and categorical variables, respectively.

In-hospital (that is, post-procedural) outcomes will be assessed by comparing the proportion of post-procedural events between prasugrel and clopidogrel groups. These crude unadjusted binary proportions will be performed using a Chi-square test between groups.

The primary endpoint of interest is the first occurrence of MACE within 90 days from date of index PCI. For purposes of this primary analysis, event-free patients will be censored at 90 days or last contact, whichever comes first. For the primary outcome of interest, the crude unadjusted 90-day rates of MACE will be calculated for each group using the *Kaplan-Meier method, also including index hospital events*. Crude rates will be compared between groups using the logrank test (Kalbfleisch et al. 1980; Prentice et al. 1978).

To evaluate the adjusted associations between treatment group (therapy initiation with prasugrel versus clopidogrel) and the primary MACE outcome, hazard ratios will be calculated using Cox proportional hazards regression that are stratified by the propensity to receive either prasugrel or clopidogrel.

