5. A sensitivity analysis for the primary MACE outcome will be performed by defining exposure groups as those patients receiving the same medication at the time of PCI and at discharge. For purposes of this sensitivity analysis, dependent outcome will be restricted to out-of hospital MACE and will exclude those patients with in-hospital death.

Secondary Objectives

Analyses for the secondary clinical outcomes, including subgroups, will be performed using propensity score with stratification as outlined above with covariate adjustment as a sensitivity analysis.

Note: Section 6.2 Economic Outcomes Analyses (including Sections 6.2.1 Unadjusted Outcomes Analyses and 6.2.2 Adjusted Outcomes Analyses) will be contained in *Addendum 1: Economic Outcomes Analyses*. References in the economic section will be added to reference list along with Addendum 1.

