6.2 Economic Outcomes Analyses

6.2.1 Unadjusted Outcomes Analyses

6.2.2 Adjusted Outcomes Analyses

6.3 Bias Adjustment

Based on prior studies (Bae et al. 2014; Wang et al. 2014), significant differences in baseline and other characteristics between groups are expected. Therefore, propensity score methodology will be implemented to account for underlying bias

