The following tables will be used to derive from an accompanying data set or spreadsheet that will be used to automate the aesthetic aspects of table production.

Table Listings

Number	Table Title	Summary Statistics	Formal Analysis
1	Summary of Baseline Characteristics by therapy at PCI	n, mean, SD, Median, min, max, n (%)	χ^2 test or Fisher's exact test will be performed for categorical variables as necessary and independent sample t-test continuous variables
2	Summary of Procedural Characteristics by therapy at PCI	n, mean, SD, Median, min, max, n (%)	χ^2 test or Fisher's exact test will be performed for categorical variables as necessary and independent sample t-test continuous variables
3	Procedural Events	n (%)	χ^2 test test for proportion
4	Clinical Outcomes by therapy at PCI	KM estimation [95% CI], crude HR, Propensity-adjusted HR; Covariate-adjusted HR	log-rank test, Cox model
5	Economic Outcomes by Discharge Therapy	mean, SD, Median, min, max, 95% CI for continuous variables, n (%)	t-tests, exact tests, and/or nonparametric tests; bootstrapping; GLM for continuous variables
		KM estimation [95% CI], crude HR, HR propensity score adjusted	χ^2 test, fishers exact test, KM estimation, log rank test, Cox model for categorical variables

Figure Listings

	Title	outcome	Pop	Type of graph	Horizontal Variables	Vertical Variables	Groupings	Statistics	Facets
1	KM rates at 90 days	MACE	Full Analysis	KM	time	probability		KM Estimates	NA
1a	KM rates by Therapy at PCI at 90 days	MACE	Full Analysis	KM	time	probability	Treatment	KM Estimates	NA
2	KM rates at 1 year	MACE	Full Analysis	KM	time	probability		KM Estimates	NA
2a	KM rates by Therapy at PCI at 1 year	MACE	Full Analysis	KM	time	probability	Treatment	KM Estimates	NA

The corresponding Mock Tables are in the following section.

Table 1. Summary of Baseline Characteristics by Therapy at PCI.

	Overall (N = XX)	Prasugrel XX (XX%)	Clopidogrel XX (XX%)	Pvalue
DEMOGRAPHICS				
Age, years				x.xxx
N, N Missing	xxx,x	xxx,x	xxx,x	
Mean ± Std	x.xx ± x.xx	x.xx ± x.xx	x.xx ± x.xx	
Median	x.xx	x.xx	x.xx	
Min , Max	x.xx,x.xx	x.xx,x.xx	x.xx,x.xx	
Gender (female)	xx (x.x%)	xx (x.x%)	xx (x.x%)	x.xxx
Height (cm)				x.xxx
N, N Missing	xxx,x	xxx,x	xxx,x	
Mean ± Std	x.xx ± x.xx	x.xx ± x.xx	x.xx ± x.xx	
Median	x.xx	x.xx	x.xx	
Min , Max	x.xx,x.xx	x.xx,x.xx	x.xx,x.xx	
Weight (Kg)				x.xxx
N, N Missing	xxx,x	xxx,x	xxx,x	
Mean ± Std	x.xx ± x.xx	x.xx ± x.xx	x.xx ± x.xx	
Median	x.xx	x.xx	x.xx	

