Mean ± Std	x.xx ± x.xx	x.xx ± x.xx	x.xx ± x.xx	
Median	x.xx	x.xx	x.xx	
Min , Max	x.xx,x.xx	x.xx,x.xx	x.xx,x.xx	
At least 1 type B2/C lesion	xx (x.x%)	xx (x.x%)	xx (x.x%)	x.xxx
At least 1 lesion with moderate/severe calcifications	xx (x.x%)	xx (x.x%)	xx (x.x%)	x.xxx
At least 1 bifurcation lesion	xx (x.x%)	xx (x.x%)	xx (x.x%)	x.xxx
At least one bare metal stent	xx (x.x%)	xx (x.x%)	xx (x.x%)	x.xxx
At least one drug eluting stent (1st gen)	xx (x.x%)	xx (x.x%)	xx (x.x%)	x.xxx
At least one drug eluting stent (2 nd gen)	xx (x.x%)	xx (x.x%)	xx (x.x%)	x.xxx
PCI vessel LM	xx (x.x%)	xx (x.x%)	xx (x.x%)	x.xxx
PCI vessel LAD	xx (x.x%)	xx (x.x%)	xx (x.x%)	x.xxx
PCI vessel LCx	xx (x.x%)	xx (x.x%)	xx (x.x%)	x.xxx
PCI vessel RCA	xx (x.x%)	xx (x.x%)	xx (x.x%)	x.xxx

Table 3. In-Hospital Post-Procedural Events by Therapy at PCI.

	Overall (N=XX)	Prasugrel XX (XX%)	Clopidogrel XX (XX%)	Pvalue
MI	xx (x.x%)	xx (x.x%)	xx (x.x%)	x.xxx
Cardiogenic Shock	xx (x.x%)	xx (x.x%)	xx (x.x%)	x.xxx
Heart Failure	xx (x.x%)	xx (x.x%)	xx (x.x%)	x.xxx
CVA/Stroke	xx (x.x%)	xx (x.x%)	xx (x.x%)	x.xxx
Tamponade	xx (x.x%)	xx (x.x%)	xx (x.x%)	x.xxx
Dialysis	xx (x.x%)	xx (x.x%)	xx (x.x%)	x.xxx
Vascular Complication	xx (x.x%)	xx (x.x%)	xx (x.x%)	x.xxx
Blood Transfusion	xx (x.x%)	xx (x.x%)	xx (x.x%)	x.xxx
Bleeding event (72 hours)	xx (x.x%)	xx (x.x%)	xx (x.x%)	x.xxx

Table 4 In and Out of Hospital Post-Procedural Events by Therapy at PCI.

	Clopidogrel	Prasugrel	Unadjusted HR [95% CI]	Propensity adjusted HR [95% CI]	Covariate-adjusted HR [95% CI]
MACE ¹					
90 Day	x.xx% [x.xx%-x.xx%]	x.xx% [x.xx%-x.xx%]	x.xx [x.xx-x.xx]	x.xx [x.xx-x.xx]	x.xx [x.xx-x.xx]
1 Year	x.xx% [x.xx%-x.xx%]	x.xx% [x.xx%-x.xx%]	x.xx [x.xx-x.xx]	x.xx [x.xx-x.xx]	x.xx [x.xx-x.xx]
Death					
90 Day	x.xx% [x.xx%-x.xx%]	x.xx% [x.xx%-x.xx%]	x.xx [x.xx-x.xx]	x.xx [x.xx-x.xx]	x.xx [x.xx-x.xx]
1 Year	x.xx% [x.xx%-x.xx%]	x.xx% [x.xx%-x.xx%]	x.xx [x.xx-x.xx]	x.xx [x.xx-x.xx]	x.xx [x.xx-x.xx]
Myocardial infarction					
90 Day	x.xx% [x.xx%-x.xx%]	x.xx% [x.xx%-x.xx%]	x.xx [x.xx-x.xx]	x.xx [x.xx-x.xx]	x.xx [x.xx-x.xx]
1 Year	x.xx% [x.xx%-x.xx%]	x.xx% [x.xx%-x.xx%]	x.xx [x.xx-x.xx]	x.xx [x.xx-x.xx]	x.xx [x.xx-x.xx]
Unplanned Revascularization					
90 Day	x.xx% [x.xx%-x.xx%]	x.xx% [x.xx%-x.xx%]	x.xx [x.xx-x.xx]	x.xx [x.xx-x.xx]	x.xx [x.xx-x.xx]
1 Year	x.xx% [x.xx%-x.xx%]	x.xx% [x.xx%-x.xx%]	x.xx [x.xx-x.xx]	x.xx [x.xx-x.xx]	x.xx [x.xx-x.xx]
Bleeding					

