Procedural ASA	0=no, 1=yes	Indicate if the patient was administered aspirin at any time during index procedure
Procedural Fondaparinux	0=no, 1=yes	Indicate if the patient was administered fondaparinux at any time during index procedure
Procedural LMWH	0=no, 1=yes	Indicate if the patient was administered a lowmolecular heparin at any time during index procedure
Procedural UFH	0=no, 1=yes	Indicate if the patient was administered fondaparinux at any time during index procedure
Procedural Bival	0=no, 1=yes	Indicate if the patient was administered bivalirudin at any time during index procedure
Procedural lib/IIIa	0=no, 1=yes	Indicate if the patient was administered IIb/IIIa inhibitor at any time during index procedure
Clopidogrel loading	0=no, 1=yes	Indicate if the patient was administered a loading dose of clopidogrel

Prasugrel loading	0=no, 1=yes	Indicate if the patient was administered a loading dose of prasugrel
Ticagrelor loading	0=no, 1=yes	Indicate if the patient was administered a loading dose of ticagrelor
Discharge ACE-I or ARB	0=no, 1=yes	At the time of discharge, was the patient prescribed an ACE-Inhibitor (or ARB)
Discharge ASA	0=no, 1=yes	At the time of discharge, was the patient prescribed aspirin
Discharge bbl	0=no, 1=yes	At the time of discharge, was the patient prescribed a beta blocker
Discharge Statin	0=no, 1=yes	At the time of discharge, was the patient prescribed a statin
Discharge Clopidogrel	0=no, 1=yes	At the time of discharge, was the patient prescribed clopidogrel
Discharge Clopidogrel 75 mg	0=no, 1=yes	At the time of discharge, was the patient prescribed clopidogrel 75mg
Discharge Clopidogrel 150 mg	0=no, 1=yes	At the time of discharge, was the patient prescribed clopidogrel 150mg
Discharge Prasugrel	0=no, 1=yes	At the time of discharge, was the patient prescribed prasugrel
Discharge Prasugrel 5mg	0=no, 1=yes	At the time of discharge, was the patient prescribed prasugrel 5mg
Discharge Prasugrel 10mg	0=no, 1=yes	At the time of discharge, was the patient prescribed prasugrel 10mg
Discharge Ticagrelor	0=no, 1=yes	At the time of discharge, was the patient prescribed ticagrelor
Discharge Anticoagulant	0=no, 1=yes	At the time of discharge, was the patient prescribed an anticoagulant (warfarin; LMWH; rivoraxaban)
Multivessel disease	0=no, 1=yes	Value is 1 if number of diseased vessels > 1
Number of lesions treated	##	Total number of lesions treated during the index PCI

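### In-hospital MACE and bleeding: the SAP's specific method and its Table 3 give only a crude chi-square, while its general rule promises a propensity-stratified analysis that the undated in-hospital fields cannot support

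*SAP*

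**What the plan says.** **Objective.** SAP 4.2, objective 3: "To compare post-procedural (in-hospital) MACE and bleeding events". Protocol 3.2.2, objective 1e, similarly compares bleeding or transfusion during the index stay.

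**Specific method.** SAP 6.1, on in-hospital outcomes: "These crude unadjusted binary proportions will be performed using a Chi-square test between groups". Protocol 3.4.1 also names a chi-square test for these outcomes.

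**Planned output.** The table list in SAP 12 gives Table 3 as n (%), with a chi-square "test test for proportion" as its formal analysis. The mock-up, "Table 3. In-Hospital Post-Procedural Events by Therapy at PCI", has counts and a p-value column. Its rows are MI, cardiogenic shock, heart failure, stroke, tamponade, dialysis, vascular complication, transfusion and 72-hour bleeding. There is no row for MACE, death or unplanned revascularization.

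**General rule.** The end of SAP 6.1: "Analyses for the secondary clinical outcomes, including subgroups, will be performed using propensity score with stratification as outlined above". In-hospital outcomes are not excepted, and a covariate-adjusted model serves as the sensitivity analysis.

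**Expected imbalance.** SAP 6.3: "significant differences in baseline and other characteristics between groups are expected".

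**Data fields.** In Attachment 1 of both documents, the post-procedure MI, stroke, transfusion and 72-hour bleeding fields are coded 0/1 without an event date. In both, the Procedural UFH row reads "Indicate if the patient was administered fondaparinux at any time during index procedure", the same text as the fondaparinux row.

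**The concern.** Treatment was chosen by clinicians, not randomized. Protocol 3.1 says prasugrel's excess of major bleeding falls particularly on patients of advanced age, with low body weight, or with previous stroke or TIA. If such patients were steered towards clopidogrel, a crude comparison of in-hospital bleeding would favour prasugrel even with no drug effect, and could hide a real excess. Table 3 would attach a p-value to that comparison.

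An analyst who follows the in-hospital paragraph of 6.1 and the Table 3 shell would deliver exactly that. An analyst who follows the closing rule of 6.1 would look for a propensity-stratified estimate, and would find neither a suitable model nor a table cell to hold it.

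**Working it through.** **1. The instructions side by side.**

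| Place | Method for in-hospital events |
|---|---|
| SAP 6.1, in-hospital paragraph | Crude chi-square |
| SAP 12, table list, Table 3 | n (%), chi-square |
| SAP 12, mock Table 3 | Counts and one p-value; no adjusted column |
| SAP 6.1, secondary objectives | Propensity stratification as described for the primary outcome |
| Protocol 3.4.1, opening | Unadjusted and adjusted, including for procedural differences |
| Protocol 3.4.1, in-hospital paragraph | Chi-square |

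**2. Can the general rule be carried out as written?** The outcome model it refers back to is a Cox regression with study center as a covariate and propensity group as the stratification variable. Cox regression needs a time to event. The post-procedure fields give only yes or no. An index-stay event can be bounded by the PCI and discharge dates, but no rule turns that into an event time. The strata can be reused for a binary outcome; the model cannot.

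**3. How large could the confounding be?** The documents give no in-hospital event rate and no expected imbalance, so there is no plan figure to reproduce. Only n = 4,303 per group comes from the plan (SAP 6.8, where it is set for 90-day MACE). Everything else here is an assumption: one binary risk feature with prevalence p_C = 20–30% on clopidogrel and p_P = 5–10% on prasugrel, a risk multiplier h = 1.5–2.5, no drug effect, and a two-sided 0.05 test.

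Crude risk ratio = [1 + p_P(h − 1)] / [1 + p_C(h − 1)]

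- Mildest corner (p_C 0.20, p_P 0.10, h 1.5): 1.05/1.10 = 0.955
- Middle case (0.25, 0.10, 2): 1.10/1.25 = 0.880
- Most extreme corner (0.30, 0.05, 2.5): 1.075/1.45 = 0.741

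The chance that the crude test rejects is Φ((d − 1.96·SE0)/SE1) + Φ((−d − 1.96·SE0)/SE1). Here d is the risk difference, SE0 the pooled and SE1 the unpooled standard error. For the middle case with 5% risk on clopidogrel, the prasugrel risk is 0.05 × 0.88 = 0.044. Then d = −0.006 and SE0 ≈ SE1 ≈ 0.00456, so the chance is Φ(−3.28) + Φ(−0.65) ≈ 0.26.

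| Risk on clopidogrel (assumed) | Mildest | Middle | Most extreme |
|---|---|---|---|
| 2% | 6.1% | 13.0% | 45.0% |
| 5% | 7.8% | 26.0% | 83.6% |
| 8% | 9.6% | 39.3% | 96.5% |

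The nominal value is 5%. With a slight imbalance the problem nearly vanishes. If prevalence is 25% versus 20%, the multiplier 1.5 and the risk 2% in patients without the feature, the crude risk ratio is 1.125/1.10 = 1.023, and the test rejects 5.3% of the time.

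**4. Procedural drugs.** Aspirin, fondaparinux, LMWH, UFH, bivalirudin and IIb/IIIa inhibitors are collected and shown in mock Table 2. None is named in the covariate list of SAP 6.1. The propensity model's clause on variables agreed to relate to outcome or exposure could admit them but does not commit to it.

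**The case against.** The strongest reply is that adjustment is already planned. The chi-square paragraph can be read as the crude step, parallel to the Kaplan-Meier and log-rank step for the primary endpoint, with the closing rule of 6.1 supplying the adjusted analysis. SAP 6.1 also says the outcome analysis plan will be finalized and documented before any outcome analysis. And "Table 4 In and Out of Hospital Post-Procedural Events by Therapy at PCI" reports propensity-adjusted and covariate-adjusted hazard ratios for MACE and bleeding.

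Much of this stands. A reader might infer that the SAP plans no adjustment at all for in-hospital events; the closing rule rules that out. Nor is Table 3 shown to be the study's main bleeding comparison, because SAP objective 2 covers bleeding in and out of hospital. The reply still does not close the gap. The general rule names no model for a binary outcome and no table displays one. Table 4 answers a different question, at 90 days and 1 year, and has no transfusion row. The only bleeding date collected belongs to a hospitalization for bleeding, so the route by which undated index-stay bleeds would enter a Cox model is itself unstated.

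A reader might also infer that procedural antithrombotics are excluded from adjustment. They are unnamed, not excluded. There is also a case against adjusting for them routinely: exposure includes patients already taking the drug or loaded around the procedure, so anticoagulant and IIb/IIIa choices may be made with or after the P2Y12 agent.

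On the UFH field, a reader might infer that heparin exposure has been lost and fondaparinux counted twice. That would follow only if sites extracted the field literally. The field name says UFH, mock Table 2 lists the two drugs separately, most sites use CathPCI definitions, and SAP 7.1 promises sites detailed technical instructions.

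**Conclusion.** The point holds as an unresolved conflict within the SAP. For a listed secondary objective, the specific method and the displayed output are crude, the general rule is adjusted, and the adjusted model it refers to cannot be fitted to the fields collected. Carried out as specified and laid out, Table 3 would be a confounded treatment comparison with a p-value.

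The size of the bias cannot be derived from the documents. The crude risk ratio of 0.741 to 0.955 with no drug effect rests entirely on the assumed prevalences and multiplier. Its direction, favouring prasugrel, rests on the assumption that high-bleeding-risk patients were steered to clopidogrel. The figures show that the bias could be material, not that it will be.

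The Procedural UFH definition is wrong in both attachments. This is a separate, smaller matter whose consequences depend on how sites extracted the field.

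**What to change.** - **SAP 6.1:** for in-hospital outcomes, specify Cochran-Mantel-Haenszel or logistic regression within the planned propensity strata, with center as a covariate in the logistic model. Report an adjusted odds ratio with 95% CI. Keep the crude percentages as description.
- **Table 3 and the table list:** add the adjusted column and an in-hospital MACE row. State how that row is derived: Attachment 1 has post-procedure fields for MI and stroke but none for unplanned revascularization during the index stay.
- **Procedural anticoagulants and IIb/IIIa use:** show adjustment for these only as a sensitivity analysis for bleeding and transfusion, and give the reason.
- **Both attachments:** correct the Procedural UFH definition to unfractionated heparin, and confirm with each site how the field was extracted.

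The cost is a few sentences of SAP text, one table column, one row and one site query. The adjusted interval will be slightly wider than the crude one. The strata are already planned, so no new propensity work is needed.

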6.2 Economic Outcomes Analyses

6.2.1 Unadjusted Outcomes Analyses

6.2.2 Adjusted Outcomes Analyses

6.3 Bias Adjustment

Based on prior studies (Bae et al. 2014; Wang et al. 2014), significant differences in baseline and other characteristics between groups are expected. Therefore, propensity score methodology will be implemented to account for underlying bias

6.4 Populations of Interest

Associations for the primary MACE outcome will be examined in the pre-defined clinical subgroups of interest as described in Section 5.3. Stratum-specific hazard

ratios will be calculated within each subgroup using Cox proportional hazards regression with propensity score stratification. Formal interaction testing will be performed between the main effects of subgroup (yes/no) and treatment allocation (prasugrel versus clopidogrel) on the primary MACE endpoint. Interaction terms with p-value <0.05 will be considered significant.

6.5 Multiplicity

The primary endpoint of interest in the present study is 90-day MACE, for which a Type I error rate of 0.05 will be used. All other endpoints are secondary and therefore no multiplicity adjustments will be performed.

6.6 Missing Data

We anticipate that the amount of missing data will be minimal in the present study as we are specifically asking sites to ensure that the data elements being requested are available.

In the instance that baseline clinical or procedural data are missing we will impute values using multiple imputation.

Missing outcome data will not be imputed.

In case the academic centers selected provide data sets where some units have incomplete observations we will use multiple imputation [Rubin (1987)] and we will perform the analysis under the assumption of data missing at random.

6.7 Robustness

The primary analysis will involve Cox proportional hazards regression as described above with stratification by propensity strata. Multiple secondary analyses will be performed as described above to examine the overall consistency of our primary findings.

These additional analyses are meant to be confirmatory (that is, yield approximately the same answer) to the primary analysis.

6.8 Sample Size and Power Considerations

Study B020 is designed to assess the difference in MACE associated with prasugrel versus clopidogrel in patients presenting with ACS managed with a PCI from academic centers in the US from 01 January 2010 to 30 June 2013. Data from the Premier study and from TRANSLATE-ACS have suggested that the MACE rate at 90 days will be approximately 8.0%. Using 8.0% as the control rate, it is expected that the relative reduction with prasugrel will be 20% lower than with clopidogrel (hazard ratio 0.80). To achieve 80% power with an alpha of 0.05, and factoring in a 10% patient drop-out, at least 4,303 patients on prasugrel and clopidogrel need to be enrolled, yielding a minimum sample size of 8,606 patients. If it is necessary to extend the window of time beyond 30 June 2013 in order to enroll an adequate number of patients, no protocol amendment will be required.

7 General Considerations

